e) To compare CRs based on infection status determined by novel					
polymerase chain reaction (PCR)-based and standard microscopic					
diagnosis					
f) To assess potential differences in susceptibility to the treatment					
regimen between the hookworm species, Necator americanus ,					
novel PCR-based diagnosis					
g) To characterize T. trichiura strains from different epidemiological					
settings and investigate potential resistance markers using a deep					
sequencing analysis					

	 h) To determine optimal timing for measuring anthelmintic efficacy in T. trichiura infection i) To evaluate potential benefits from deworming on morbidity indicators and nutritional parameters j) To determine an exposure (including length of time that the drug concentration is above the minimal inhibitory concentration (MIC), Cmax, area under the curve (AUC))-response correlation of ivermectin and albendazole in school-aged children 					
Study design	Double blind, randomized controlled trial					
Study product / intervention	Administration of a single oral dose of ivermectin + albendazole					
Comparator(s)	main trial: albendazole (400 mg) monotherapy, DF study: placebo					
Key inclusion / Exclusion criteria	 T. trichiura with at least two slides of the quadruple Kato-Katz thick smears positive and infection intensities of at least 100 eggs per gram of stool (EPG), agreeing to comply with study procedures, including provision of two stool samples at the beginning (baseline) and on three follow-up assessments (approximately 3 weeks, 6 months, and 12 months later), written informed consent signed by parents and/or caregivers for children/adolescents; and written assent by child/adolescent (aged 6-20 years). Exclusion: No written informed consent by individual/parents and/or caregiver, any clinically relevant abnormality (including severe anemia or clinical malaria) or history of acute or severe chronic disease (e.g. cancer, diabetes, chronic heart, liver or renal disease), recent use of anthelminthic drug (past 4 weeks), attending other clinical trials during study, negative diagnostic or low egg count (less than 100 EPG or less than 2 out of 4 slides positive) result for T. trichiura, known allergy to study medication, pregnancy or lactating in the 1st week after birth, taking medication with known interaction on study drugs. 					

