	Each participant will be asked to provide a finger-prick blood sample for hemoglobin measurement, a rapid diagnostic test (RDT) for Plasmodium spp. and where applicable a biplex RDT for lymphatic filariasis/onchocerciasis at baseline and 6 and 12 months after treatment. At the same time points anthropometric measurements (i.e. height, weight, mid-upper arm circumference (MUAC) and skinfold thickness) will be taken for all participants. In addition, a venous blood sample (~8 ml) will be taken from each participant to assess biochemical blood parameters as proxies for vital organ functioning (e.g. complete blood count, urea, creatinine, transaminases etc.) and nutritional indicators for micro- (i.e. (pro-) vitamins, inflammation markers, and iron/ferritin) and macronutrient (i.e. albumin) deficiencies at baseline, day 21, day 180 and day 360.				
	To all participating households, a questionnaire will be administered assessing information on socioeconomic characteristics and access to sanitation, water facilities, and hygiene behavior.				
	For the assessment of pharmacokinetic parameters within the DF study the participating school-aged children (6-12 years) will be sampled using finger pricking for microsampling at 0, 1, 2, 3, 4, 5, 6, 7, 9, 24, 48 hours post-dosing.				
Statistical Analyses	An available case analysis will be performed, including all subjects with primary end point data. Supplementary, a per-protocol analysis will be conducted. CRs will be calculated as the percentage of egg-positive subjects at baseline who become egg-negative after treatment. Differences among CRs (between treatment arms and between diagnostic approaches) will be analysed by using crude and adjusted logistic regression modeling (adjustment for age, sex and weight).				
	Geometric and arithmetic mean egg counts will be calculated for the different treatment arms before and after treatment to assess the corresponding ERRs. Bootstrap resampling method with 5,000 replicates will be used to calculate 95% confidence intervals (CIs) for differences in ERRs.				

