5.3 Exclusion criteria

- 1. No written informed consent by individual/parents and/or caregiver.
- Presence of major systemic illnesses, *e.g.* severe anemia (below 80 g/l Hb according to WHO [30]), clinical malaria as assessed by a medical doctor (positive *Plasmodium* RDT and ≥38 °C ear temperature), upon initial clinical assessment.
- 3. History of acute or severe chronic disease (e.g. cancer, diabetes, chronic heart, liver or renal disease).
- 4. Recent use of anthelmintic drug (within past 4 weeks).
- 5. Attending other clinical trials during the study.
- 6. Negative or low egg count (less than 100 EPG or less than 2 out of 4 slides positive) diagnostic result for *T. trichiura* eggs in the stool.
- 7. Known allergy to study medications (i.e. albendazole and ivermectin).
- 8. Pregnancy or lactating in the 1st week after birth (according to WHO guidelines within LF control programs [31]).
- 9. Currently taking medication with known interaction (*e.g.* for albendazole: cimetidine, praziquantel and dexamethasone; for ivermectin: warfarin).

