7.2 Justification of number of trial subjects

Parallel group multi-country study

Based on available summarized efficacy measures from a recent review [1] and the published literature, we assume that the CR of albendazole against *T. trichiura* is 30% compared to 50% in the albendazole-ivermectin treatment regimen. To detect a difference with 90% power at a two-sided 5% significance level, we require 121 participants per study arm and 143 to account for potential loss to follow-up of 15%. We further assume the same treatment efficacy in the mid-term treatment and a 6-months reinfection risk of 10%. Consequently we expect a proportion of negative patients after 12 months of 44% in the albendazole arm and of 65% in the albendazole-ivermectin arm resulting in a required sample size of 111 participants per arm. To account for a loss to follow-up of 30% after 6 months and 40% at final assessment (12 months) we aim to recruit 300 participants in each treatment group (600 in total) in each country.

Subgroup analysis will be conducted stratifying the study population by age category (school-aged and adults). For the subgroup analysis we will pool the data from all 3 countries to ensure sufficient statistical power.

DF study

Since the existence of a drug effect is well known, the main aim of the study is the elucidation of the nature of the dose–response relationship. Modeling approaches showed that with 40 children enrolled in each of the 4 study arms (placebo, 200 μ g/kg, 400 μ g/kg, and 600 μ g/kg co-administered with albendazole (400 mg)) the dose response prediction model had a median precision (one half length of the 95%-confidence intervals) of 10% assuming associated cure rates of 2.5%, 50%, 60% and 70% taking into account a loss to follow up of 10%. The suggested sample size is also in line with the recommendations from *Klingenberg et al. 2009* [36]. This sample size is sufficiently high to determine the key PK parameters as well as pharmacokinetic/pharmacodynamic (PK/PD) relationships taking into account that PK variability is high.
Page 37 of 176

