alternative = "two.sided", midp = T)

This analysis has been chosen because most biomedical journals prefer the absolute difference over the relative difference. However, adjustment for confounder or effect modifier is not possible; therefore, the adjusted analysis will use standard logistic regression.

Egg reduction rates (geometric mean based) will be calculated using the following formula

$$ERR = 1 - \frac{\frac{1}{n}e^{\sum \log(EPG_{follow} - up + 1)}}{\frac{1}{n}e^{\sum \log(EPG_{baseline} + 1)} - 1}$$

Differences in geometric mean based ERR will be analysed via bootstrap resampling using the following code

}

library(boot) difgm <- boot(data = d, statistic = diffgm, R = 2000, strata = d\$arm)

The arithmetic based ERR will be estimated in the same way.

If the sample size of study participants infected with hookworm, Ascaris lumbricoides and *Strongyloides stercoralis* is considered sufficiently large, efficacy against these parasites will be assessed in the same way. If the number of participants will be below 100 per arm the trial arms will only be compared descriptively.

Page 173 of 176

Efficacy results and estimates will be presented as outlined below

		Pemba Is	land	Côte d'Iv	oire	Lao PDR		Total		
Variab	le	ALB (n=xxx)	IVM- ALB (n=xxx)	ALB (n=xxx)	IVM- ALB (n=xxx)	ALB (n=xxx)	IVM- ALB (n=xxx)	ALB (n=xxx)	IVM- ALB (n=xxx)	
T. trich	iura									
No. of p	participants positive	for								
infectio	n Defere									
	treatment									
	After treatment									
Cure ra	te. % (95% CI)									
No. of p	participants cured n	(%)								
1	From light									
	From moderate									
	infection									
	From heavy									
Carrier	infection									
Geomet	tric mean EPG									
	Before									
	After treatment									
GMEg	g_reduction rate									
% (95%	CI)									
Arithme	etic mean EPG									
	Before									
	treatment									
	After treatment									
AM Eg	g-reduction rate,									
% (95%) A lumb	o CI) bricoid e s									
N partic	cinants positive									
T partic	Before									
	treatment									
	After treatment									
Cure ra	te, %									
N partic	cipants cured (%)									
1	From light									
	infection									
	From moderate									
	infection									
	From heavy									
Geomet	tric mean EPG									
	Before									
	treatment									
	After treatment									
Egg-red	luction rate, %									
Hookw	orm									
N partic	cipants positive	1								
	i 1			1		1		1		

Page 174 of 176

	Before					

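### The count that qualifies a participant is also the egg reduction rate baseline, so regression to the mean modestly inflates each arm's rate and shrinks the difference between arms

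*Combined protocol and SAP*

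**What the plan says.** All protocol versions set the same entry rule. The synopsis of the Swiss-approved protocol requires "at least two slides of the quadruple Kato-Katz thick smears positive and infection intensities of at least 100 eggs per gram of stool (EPG"). Section 5.3 excludes the complement: "Negative or low egg count (less than 100 EPG or less than 2 out of 4 slides positive) diagnostic result".

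The schedules of visits (section 4.6 of each protocol; Time and Events Table in the SAP) list one stool examination before treatment, at day -21 to -1, and none at hour 0. Sections 4.3.2 and 7.3 compute eggs per gram (EPG) as the sum of the four slides times six.

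On the ERR, the protocols state: "Geometric and arithmetic mean egg counts will be calculated for the different treatment arms before and after treatment to assess the corresponding ERRs". Section 7.3 adds bootstrap intervals for each ERR and for the difference between them. The SAP efficacy section says: "Differences in geometric mean based ERR will be analysed via bootstrap resampling", and treats the arithmetic version in the same way. ERR against *T. trichiura* is the first listed secondary endpoint.

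The SAP results table shows geometric and arithmetic mean EPG before and after treatment, by arm, per country and in total. No between-arm estimate with an interval is planned on the day-21 counts. Regression to the mean, a second baseline count and a baseline-adjusted egg-count model are not mentioned.

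**The concern.** A baseline that had to reach 100 EPG is a selected reading; the day-21 count has no such threshold. Where counts vary within a person and some people lie near the cut-off, the baseline mean of those enrolled overstates what a fresh untreated count would show.

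Randomisation makes this overstatement equal in both arms in expectation, so it is easy to assume that it cancels. It does not cancel in a difference of ERRs, because it acts as a multiplier. The bootstrap resamples the same selected baselines and so reproduces the bias. At stake are the reported ERR for albendazole, which comes out too high, and the added benefit of ivermectin on egg output, which comes out too low.

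**Working it through.** **The plan's own figure.** The documents give no power or expected value for the ERR difference. The sample size rests on cure rate: albendazole "is 30% compared to 50% in the albendazole-ivermectin treatment regimen". Section 7.2 says: "To detect a difference with 90% power at a two-sided 5% significance level, we require 121 participants per study arm". With unpooled variance, (1.960 + 1.282)² × (0.3×0.7 + 0.5×0.5) / 0.2² = 120.8, so 121; then 121/0.85 = 142.4, so 143. Both reproduce (a pooled variance gives 124). Neither uses the baseline mean, so neither changes.

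**Threshold.** 16 eggs × 6 = 96 and 17 × 6 = 102, so entry needs at least 17 eggs over four slides.

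**Algebra.** Let k be the mean of a fresh untreated count in the enrolled, divided by the mean of the count that enrolled them. Then, for either type of mean:

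- observed ERR = 1 − k × (1 − true ERR)
- inflation = (1 − k) × (1 − true ERR), largest where most eggs remain
- observed ERR difference = k × true difference
- (1 − ERR combination)/(1 − ERR albendazole) does not involve k

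**Size of k (assumed).** A simulation applied the trial's entry rule to two stools of two slides. It used log-normal person means with log SD 1.4, day-to-day log SD 0.4 to 1.0, extra slide-to-slide variation, and an enrolled geometric mean of about 361 to 506 EPG. It gave k of about 0.69 to 0.95 for the geometric mean.

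A second error model took the between-person spread from the background Table 2: √(2 ln(1059/489)) = 1.24 and √(2 ln(4948.1/550.0)) = 2.10. It gave k of 0.69 to 0.96 at a day-to-day CV of 0.5 to 0.8, and 0.47 to 0.78 at a CV of 1.2. For the arithmetic mean, that model gave k of about 0.94 to 1.0 in most scenarios and 0.78 to 0.89 in the worst.

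**Points at the plan's cure rates.** Cured people enter the geometric mean as log(0+1) = 0. Take an unselected baseline geometric mean of 400 EPG for illustration, 30% cured on albendazole and 50% on the combination. Assume that uncured people keep 50% or 80% of output on albendazole and 15% on the combination. I use the usual geometric mean with the +1 offset.

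| Arm | Day-21 geometric mean | True ERR |
|---|---|---|
| Albendazole, uncured keep 50% | 201^0.7 − 1 = 39.9 | 90.0% |
| Albendazole, uncured keep 80% | 321^0.7 − 1 = 55.8 | 86.0% |
| Combination, uncured keep 15% | 61^0.5 − 1 = 6.8 | 98.3% |

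- k = 0.95, uncured keep 50%: albendazole 90.0 → 90.5 (+0.5). Difference 8.3 → 7.9 (−0.4).
- k = 0.69, uncured keep 80%: albendazole 86.0 → 90.4 (+4.3). Difference 12.3 → 8.5 (−3.8). The combination moves only 98.3 → 98.8.

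Across the simulated scenarios, the true albendazole ERR is about 84 to 91% and is overstated by about 0.4 to 5 points. The difference shrinks by about 0.3 to 4.4 points, which is 1 − k, or 5 to 31%, of its value. The arithmetic-mean difference shrinks by about 0.1 to 3.3 points.

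**The case against.** The strongest reply is that the effect is small and harmless. Three parts of it stand.

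- **Size.** A reader might put the background's 49.9% albendazole ERR and 91.3% combination ERR into the algebra: 41.4 × 0.69 = 28.6, a loss of almost 13 points. The documents do not support that for the geometric mean. The 49.9% does not state its type of mean. At the planned 30% cure rate, with no reduction in anyone else, 401^0.7 − 1 = 65.4 against 400 is already an ERR of about 84%. A geometric-mean albendazole ERR near 50% is therefore not attainable. On the arithmetic scale, where 50% is plausible, k is usually close to 1.
- **Day-21 data.** A reader might infer that the plan never sets the arms side by side on day-21 counts. It does: the SAP results table prints those means by arm. Only a formal contrast with an interval is missing.
- **Consequence.** A reader might fear a false claim of benefit. With equal arms, k leaves a zero difference at zero, and otherwise the bias runs against the combination.

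Two counter-arguments do not remove the point. Stratifying on baseline intensity balances k between arms but does not bring it to 1. Comparability with earlier ERRs is a reason to keep the ERR, not to leave the bias unstated.

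**Conclusion.** The point holds, at moderate size. The direction is certain whenever k is below 1; the magnitude is an assumption, because the documents give no within-person variation. The point figures also depend on the plan's cure rates and on the assumed output of uncured people. A lower albendazole cure rate leaves more eggs and enlarges them, while the proportional loss stays at 1 − k.

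The primary endpoint does not use the baseline mean. In the simulation, at most 0.4% of untreated enrolled people read egg-negative on re-measurement. The recruitment target ("we aim to recruit 300 participants in each treatment group (600 in total) in each country") needs no change. A reader might also infer that the ERR difference should be withdrawn or demoted. That is not needed: it remains a valid test of no difference and only its estimate and interval are shifted.

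**What to change.** In the SAP efficacy section, keep each arm's ERR and the ERR difference as planned, and add:

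1. The ratio of day-21 geometric mean EPG, combination over albendazole, per country, with a bootstrap 95% CI. The selected baseline does not enter it. Adjustment for log baseline EPG is optional. With 30 to 50% zeros expected, a linear model of log(EPG+1) depends heavily on the offset, so it should not be required.
2. A note that the ERRs and their difference include regression to the mean from the 100-EPG entry rule.

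This uses data already collected and takes a few lines of text. The cost is one more reported number. As with the geometric-mean ERR, the ratio depends on the +1 convention and partly reflects the cure difference.

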4.1 Primary and secondary endpoint

T. trichiura infection status assessed by Kato-Katz 14-21 days after treatment will be the primary endpoint and the main outcome for efficacy be expressed as cure rate (CR) (*i.e.* conversion from being egg positive pretreatment to egg negative post-treatment) and egg reduction rate (ERR) (secondary end point). Secondary endpoints include further infection status with *A. lumbricoides*, hookworm and *S. stercoralis* and related efficacy measures, adverse events, infection status assessed by PCR and key pharmacokinetic parameters in school-aged children. In addition, optimal timing for drug efficacy assessment in *T. trichiura* infection will be determined, *T. trichiura* strains will be described and potential resistance markers evaluated using deep sequencing and potential benefits on nutritional and morbidity indicators from treatment assessed (exploratory end points).

4.2 Type of trial

Double blind randomized controlled trial.

4.3 Trial design

4.3.1 Baseline survey and screening

Parallel group multi-country study

A randomized-controlled trial will be conducted with two treatment arms to be followed-up over a 12 months period with an intermediate re-treatment of participants found re-infected after 6 months (Figure). This parallel group trial will be conducted as a multi-country study; thus, in each setting a separate trial according to the design described below will be set up, to provide a better basis for the subsequent generalization of its findings. This arises from the possibility of recruiting the subjects from a wider population and of administering the medication in a broader range of clinical settings, thus presenting an experimental situation that is more typical of future use. The study includes one baseline and three follow-up assessments at 3 weeks (day 21), 6 months (day 180), and 12 months (day 360).

Figure 2. Design and timeline of the randomized-controlled trial to be implemented in each of three settings.

The study is designed as a two-armed trial including one arm with a single drug administration (arm A; albendazole) and one arm with combined treatment through co-administration of separate tablets (arm B; albendazole and ivermectin).

The trial will be conducted as a multi-country study with two settings in Africa and one in Asia, namely Côte d'Ivoire, Pemba (Zanzibar, Tanzania) and Lao PDR.

At baseline, all participants will be asked to provide two stool samples of at least 15 grams each (within a maximum of 5 days). From every stool specimen, duplicate Kato-Katz thick smears (41.7 mg each) [15] will be prepared and read under a microscope for eggs of T. trichiura, A. lumbricoides and hookworm by experienced technicians. A small amount of feces (~10 mg and 60 µg, respectively) will further be tested on fecal occult blood and calprotectin as proxies for gut morbidity and inflammation using a rapid diagnostic test an immunoassay, respectively [16]. Additionally, a portion of 1.5-2 g of stool from each specimen will be preserved in 70% ethanol and shipped to a reference laboratory at the Swiss Tropical and Public Health Institute (Swiss TPH, Basel, Switzerland) for PCR analysis [17]. While discrimination of hookworm species via morphological comparison during microscopy of Kato-Katz slides is not feasible [18], PCR will allow to accurately determining efficacy and for further classification of hookworm infection into the three species N. americanus, A. duodenale and A. ceylanicum. The remains of each stool sample (ideally 10 to 20 g) will be processed by the Baermann technique for identification of S. stercoralis infections and be recorded qualitatively as larvae-positive or negative. At baseline and in the first follow-up (3 weeks post treatment) an additional portion of the second stool sample (1.5-2 g) from a subsample of 10 participants identified with heavy intensity infections in each case (as assed on the first sample) will be preserved in 95% ethanol, shipped to the same reference laboratory at Swiss TPH in Switzerland and subjected to deep sequencing for characterization of T. trichiura strains and

Page 25 of 176

investigation of potential resistance markers [19]. A subsample of 30 participants will be asked to provide a daily stool sample for a period of up to 4 weeks to monitor dynamics of *T. trichiura* egg output for subsequent determination of the optimal timing for drug efficacy assessment as has been done for other STH species earlier [20].

A subsequent independent quality control of sample results (approximately 10%) will be conducted. Results are considered correct if the following tolerance margin is not exceeded: (i) No difference in presence/absence of hookworm, *A. lumbricoides* and *T. trichiura*, (ii) egg counts are +/-10 eggs for counts \leq 100 eggs or +/-20% for counts >100 eggs (for each species separately) [21]. In case discrepancies above the tolerance margin are noted in one or more slides, all slides are re-read by the local technicians. The new results are discussed, so that in case of discordant results, slides can be re-evaluated to reach consensus. Infection intensity expressed as the arithmetic and geometric mean egg count per gram of stool (EPG) will be calculated for each treatment arm. All microscopically analyzed quadruplicate Kato-Katz thick smears will be destroyed within one day (after passing the quality control). The same sampling procedure and diagnostic approach will be applied at days 21, 180 and 360 post-treatment.

Patients with filariasis showed significantly higher numbers of adverse events (AE) for treatment with ivermectin in combination with albendazole in earlier studies [22-24]. A rapid diagnostic test (RDT; *i.e.* SD BIOLINE Oncho/LF IgG₄ biplex test) to detect antigens in the blood will therefore be used to identify potential co-infection with *Wuchereria bancrofti* and *Onchocerca volvulus* at baseline, 6 and 12 months post-treatment (before a potential re-treatment). AEs after treating filariasis were mostly mild [3]; the approach of capturing AEs will thus not change but the result of the RDT be used to explain potential differences in AE reporting between filariasis negative and positive participants.

A clinical examination of the study participants assessing general health, anthropometric parameters including height, weight, mid-upper arm circumference (MUAC) and skinfold thickness (i.e. triceps and subscapular skinfolds) as well as tympanic temperature using an ear thermometer will precede the treatment and will be repeated on two follow-up assessments (days 180 and 360) to evaluate potential benefits from deworming. Each participant will be asked to provide a finger-prick blood sample for a RDT for *Plasmodium* spp. infection and to evaluate hemoglobin (Hb) levels using a HemoCue analyzer (Hemocue Hb 301 system; Angelholm, Sweden) following the same (re-)assessment schedule. To assess potential improvement on nutritional indicators for micro- (*i.e.* (pro-) vitamins, inflammation markers, and iron/ferritin) and macronutrient (*i.e.* albumin) deficiencies and dynamics of biochemical blood parameters as a proxy for functioning of vital organs a venous blood sample (approximately 8 ml) will be taken at baseline, day 21, day 180 and 360. The biochemical parameters to be assessed include urea, creatinine, bilirubin, azotemia, Alanine Amino Transferase (ALAT), Aspartate Amino Transferase (ASAT) as well as blood cell counts (*e.g.* hematocrit, erythrocytes and platelets). To avoid accidental treatment of pregnant girls/women all female participants (\geq 10 years) will be asked to provide a urine sample of at least 10 ml to be subjected to a pregnancy RDT on day 0 and day 180.

All trial participants will further be asked about existing clinical symptoms before drug administration. Additionally, they will be asked to provide subjective short-term (*e.g.* convenience of treatment) and long-term (*e.g.* effectiveness in reducing symptoms) treatment satisfaction embedded in the re-assessment questionnaires. As a measure of patient-rated physical functioning and wellbeing all children (6-16 years) will be administered a questionnaire before, 6 and 12 months after treatment, based and adapted from tools already validated in schoolaged children from rural settings in Côte d'Ivoire [25] and pre-tested in a comparable school-aged population not otherwise involved in this trial. To adjust for known influencing factors with regard to reinfection and morbidity [26, 27] in the subsequent analysis and to identify risk factors for residual infections [28] a household-based questionnaire will be administered to one adult member of each participating household, assessing information on socioeconomic characteristics, access to sanitation and water facilities as well as hygiene behavior.

DF study with school-aged children

Embedded in the parallel group trial a randomized-controlled DF study assessing ascending doses of ivermectin co-administered with a single dose of albendazole will be implemented. The study is designed as a four-armed trial including ascending doses of ivermectin co-administered with the standard dose of albendazole (arm 1–3) and one placebo arm serving as a comparator (arm 4) (Figure). 160 school-aged children infected with *T*. *trichiura* will be randomly assigned to arm 1–4. Baseline and screening procedures are identical to the parallel group study. Children in arm 1-3 will be micro sampled on different time points between treatment day 0 and day 2 (at 0, 1, 2, 3, 4, 5, 6, 7, 9, 24, 48 hours post-dosing) in order to obtain pharmacokinetic data while children in arm 4 will provide finger-prick blood samples at day 0 only for RDT assessments.

Figure 3. Efficacy, safety and pharmacokinetics of ivermectin-albendazole co-administration: dose-finding study flow.

